11.0 Sharing of Results with Research Participants

Individual test or research results will be shared with research participants (this is not referring to sharing through standard academic channels, e.g., publishing, presentation, etc.):

Yes No

If yes, describe how the results will be shared. Participants will be invited to review their daily spending surveys to help monitor spending on out-of-pocket costs of caregiving. Recording daily spending is a part of the intervention itself, regardless of study participation. (Non-study participants receive a worksheet to monitor spending.) By sharing daily spending survey,

participants can use information they already shared in surveys for this activity. Spending surveys will be emailed to participants using PDF downloads from REDCap of their daily surveys. We will also share aggregate findings with participants at the end of this study

Individual test results will be shared with others (e.g., lab results given to a primary care physician):

Yes No

If yes, describe with whom and how the results will be shared. [Click here to enter text.](#)

12.0 Study Design/Procedures

Directions:

- 1) Describe the overall study design (e.g.: single visit, single-blind, double-blind, non-randomized, randomized, blood draw, investigational drug, device etc.).**
- 2) Provide a description of all study-related research procedures being performed, including the length of time involved.**
- 3) Include procedures being performed to monitor research participants for safety or minimize risks.**
- 4) Describe the source records including medical or educational records, which will be used to collect data about subjects.**
- 5) Include a description of any device being used to collect data (e.g., eye tracker, step counter). If the device itself is being studied, include additional information in Section 29.**

Overall. This study uses a single arm pre- and post-test design with three data collection points (baseline and two follow up) to evaluate the preliminary efficacy, acceptability, and feasibility of delivering an intervention to lower the out-of-pocket spending on caregiving for Latino caregivers to persons living with dementia. Data will be primarily collected using survey research methods, including “daily diary” methods (N=60). We also plan to collect qualitative semi-structured interviews with participants (N=15), as well as fidelity information about the delivery of the intervention. Participation will take approximately 10 weeks from baseline to completion. **Enrollment.** Participants will enroll in the CONFIDENCE program using an Eventbrite link that will be shared as a part of regular services offered by the University of Southern California Family Caregiver Support Center. When a participant registers for the CONFIDENCE program, they will be asked if they are interested in participating in the research study. Participation in the research study is optional; caregivers do not need to enroll in the study to attend the program. If a caregiver indicated interest in this research, the research assistant or PI will reach out by phone and email (up to 4 contacts) to tell the caregiver more about the study and determine eligibility. The participant may choose to complete the eligibility form online or by phone. Even if the participant completes the eligibility form online, they will receive a follow up call to ensure they understand the study activities and verbally consent to participate. **Intervention.** Enrolled participants will be asked to attend once weekly group-based sessions for the CONFIDENCE program by Zoom for 5 weeks. Each session will last approximately 1.5 hours each and will require participants to complete up to 1 hour of take-home activities per week. Each session will focus on a different topic (e.g., seeking community resources to displace out-of-pocket spending) meant to help caregivers displace out-of-pocket care costs and reduce financial strain. There are five sessions (5 weeks) total to the CONFIDENCE program. Sessions will be led by 2 facilitators with experience in caregiver intervention or else trained by someone with this experience. Up to 15 caregivers may register for each sessions, though we anticipate no more than 10 caregivers to attend each session due to absences.

Survey Administration. Enrolled study participants will receive a baseline survey up to 2 weeks prior to the first intervention session and will be asked to complete the survey within 7 days. The baseline survey will ask about spending on out-of-pocket care costs, financial strain, resourcefulness, self-efficacy, as well as information about the caregiving context and use of supports. It is anticipated this survey will take no more than 20 to 30 minutes to complete. Once the baseline survey is complete, participants will begin to receive daily surveys by phone or email, depending on their preferences. Daily surveys will ask about spending on caregiving that day and are to be completed from 7 pm to 11 pm each consecutive day for 5 days. These surveys will serve two purposes: 1) daily spending habits reported in surveys will be summarized and shared with back with participants as a part of the intervention and 2) data from surveys will be used to determine average daily spending, our primary outcome of interest. Daily spending surveys will take no more than 10 minutes to complete. We anticipate some participants will not meet the requested

timeline for the Baseline survey. If so, we will continue to allow them to participate in the study without complete they daily spending surveys, so long as the Baseline survey is completed prior to the first intervention session. This will enable us to still collect data about outcomes besides out-of-pocket costs of care. A follow up survey will be sent immediately after the participant completes the intervention (within 48 hours) and will also ask about participant satisfaction with CONFIDENCE. A second follow up survey will be sent 8 weeks after the intervention is complete. After the participant completes the second follow up survey, they will receive a second set of daily spending diaries administered in the same way as the first set of diaries. Follow up surveys are expected to take approximately 20 to 30 minutes to complete. Participants will receive up to 5 reminders to complete the baseline and follow up surveys, include 3 emails prompts and up to 2 phone calls. Participants will receive a text message reminder, if they choose, reminding them to complete daily spending surveys each night. **Qualitative interviews.** Up to 15 participants will also be asked to participate in a one-on-one qualitative, in-depth, semi-structured interview as well about their experiences with the program, which is expected to take approximately 45 minutes depending on how much the participant would like to share. Selection of interview participants will be based on purposeful sampling, with the goal of recruiting a qualitative sample that includes a range of care experiences according to participant gender, age, employment status, and kin relationship to the person to whom care is provided. Interviews will be completed over Zoom and recorded and later transcribed. Participants will be invited to complete this interview after completing the CONFIDENCE program. If the participant agrees to participate, they will receive a study information sheet by email prior to attending the interview and will review this information sheet before completing the interview. **Payment for surveys and qualitative interviews.** Amazon gift cards will be sent to participants by email for each study activity (surveys and interviews). We will pay participants for the baseline and first set of diaries surveys within a week of when the first set of diaries are due. A second payment will be administered within a week of the first follow up survey being completed. The remaining payments will be sent the week of the second set of diary surveys are due/completed. Payment for interviews will be sent within 1 week of completing the interview. Participants may earn up to \$125 for participating, or \$150 if they complete the qualitative interview. Participants may earn \$25 for each study activity. **Fidelity.** Fidelity will be monitored by an observer (PI or research assistant) and the CONFIDENCE program facilitators. We will monitor one randomly selected CONFIDENCE lesson for each cohort. The selected lesson will be based on Stata's random number generator. The facilitators will know in advance of each lesson if selected for monitoring so they may record lesson. The facilitator will be sent a survey within 24 hours of completing selected sessions to self-monitor delivery. Fidelity surveys will be sent by the PI using REDCap. Session recordings will be stored in the USC CONFIDENCE Office 365 Shared folder and deleted once fidelity forms are completed. The research assistant or PI will watch the recording and complete the fidelity survey within 2 weeks of the lesson taking place. **Attendance.** The USC facilitator will monitor attendance at CONFIDENCE sessions and will store this information in a shared Office 365 folder. The study team will extract information about attendance from study participants from Excel files where attendance is marked and enter it into REDCap for study participants. **Comparison of registrant demographics and study participants.** In addition to data collected from surveys, we will compare the demographic characteristics of individuals who register for CONFIDENCE to participate in the educational program alone with those of study participants. This information can help to inform future recruitment methods by helping the study team understand differences in the characteristics of those who choose to participate in research and those who do not. As a part of their funder's requirements, USC must report on demographic characteristics of program participants to the sponsor. They currently collect this information using the Eventbrite registration page. The Case Western investigators will already have access to the Eventbrite form information to identify participants who are interested in participating in the research study. To compare the characteristics of study participants to non-study participants, we will download Excel files directly from Eventbrite onto an encrypted university Box folder, and add an indicator variable to indicate whether or not individual registrants were in the research study. Once this occurs, all identifiable information will be removed from Excel files and the file will be saved so we can conduct analyses and compare characteristics of study and non-study participants. **Participant safety and monitoring adverse events.** *Adverse events.* Adverse events and protocol deviations will be recorded on an adverse event form by the study team member (PI or RA) who first observes this event. Adverse events pertaining to participant safety and confidentiality will be promptly reported by the PI by phone. Where the RA or PI suspects risk of harm to self or others, this will be reported to USC PI [name], who is a licensed clinical psychologist with extensive experience working with caregivers. [name] is the director of the USC Family Caregiver Support Program where CONFIDENCE is being administered. She will reach out to the participant by phone to conduct further assessment and a safety plan. All protocol deviations and adverse events will be promptly reported to the Institutional Review Board by the PI. Serious adverse events will be reported within 24-hours. **Data and Safety Monitoring.** The PI will complete a Data Safety Monitoring Report every 6 months of the study. The Data Safety Monitoring Report will include the following core elements: a) Progress towards enrollment and participant retention; b) Participant characteristics for enrolled and retained participants (e.g., age, race, ethnicity, gender, aspects of the caregiving situation) according to intervention status; and c) Documentation of adverse events, serious adverse events, and unanticipated problems, as defined below, including resolution of these events and study protocol modifications. This report will not contain any participant identifiers. This report will be shared with the USC PI for review.

Sub-study (8/2023 Modification): To complete the sub-study objective, the research team will draw upon existing de-identified qualitative interview data from N=14 family caregivers collected by collaborators at USC. (An Exempt approval, information sheet, interview guide, and notice indicating no need for a DUA are attached.) We will conduct a content analysis of the types of expenditures covered by participants, wherein we will report the frequency with which each expense was described. This will be reported alongside baseline data that asks about out-of-pocket spending on caregiving collected in the parent study, including frequencies and estimated costs. These survey data were informed by responses collected during qualitative interviews, which helped the researchers to generate ideas about what to ask about in surveys. By reporting out on these data in tandem using a mixed methods approach, we can provide a holistic picture of what out-of-pocket spending on care looks like for Latino family caregivers.

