days in a month and add all monthly expenses. While the measure is subject to recall bias and fluctuations in spending, it balances 1) the need to efficiently collect data and 2) reduces recall bias by relying on monthly recall alone. Analysis of Baseline and Follow Up Measures We will used two sets of paired t-tests to examine changes in scores between baseline and follow up surveys. If we discover a p-value of <0.05 after running tests, this will indicate there was a statistically significant difference between scores. We will compare scores from baseline until the first follow up survey and from baseline until the second follow up survey. In addition, we will examine mean scores at each time point, as well as the standard of deviation for all summed scores on each scaled. **Handling of Missing Data Missing daily surveys.** If participants miss a survey, we will adjust the monthly formula such that we will multiply according to the number of days for which surveys are completed to reach 30. For example, if a participant completed 4/5 surveys, we will multiply by 7.5 instead of 6. We will exclude participants who miss more than 2 daily surveys from analyses when examining monthly costs. **Missing data on follow up surveys.** Although data from all participants will be reported in sample descriptives, for all analyses using t-tests, we will use a complete case analysis such that participants with any missing data will be removed from the analytic sample. Although this approach risks missing data bias, multiple imputation and maximum likelihood estimation are not feasible to conduct with bivariate analyses. We will conduct bivariate analyses using a "dummy" variable to identify potential differences between those with complete and incomplete data and will also report the extent of missingness using frequencies and percentages.

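### Baseline diaries are timed from return of the baseline survey, not from session 1, so with shorter send leads some baseline days can fall after the program starts, while some late repliers with enough clear evenings appear to get no diaries

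*Combined protocol and SAP*

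**What the plan says.** Section 12.0 (Survey Administration) says enrolled participants "receive a baseline survey up to 2 weeks prior to the first intervention session and will be asked to complete the survey within 7 days". Diaries follow from completion of the survey: "Once the baseline survey is complete, participants will begin to receive daily surveys by phone or email", and they "are to be completed from 7 pm to 11 pm each consecutive day for 5 days".

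The section expects some late replies. For people who miss the timeline asked of them for the baseline survey, it says "we will continue to allow them to participate in the study without complete they daily spending surveys", provided the survey is done before session 1. The stated reason is that outcomes other than out-of-pocket cost can still be collected. That proviso is the only condition tied to session 1, and it concerns the survey, not the diaries.

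Section 17.0 scales diary spending to 30 days according to the number of diaries completed, and adds: "We will exclude participants who miss more than 2 daily surveys from analyses when examining monthly costs". It has no rule about the calendar date of a diary relative to session 1.

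The two sections label the outcome differently. Section 12.0 calls average daily spending from the diaries the primary outcome of interest. Section 17.0 lists monthly spending as secondary, with self-efficacy and resourcefulness as primary.

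**The concern.** The design has a single arm, so the spending result rests on a before-and-after comparison, and the first diary set is the only diary measurement meant to precede the program. The plan controls it through the 7-day reply request, which does not measure what matters: how many evenings are left before session 1.

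That can go wrong in two ways. A participant who replies on time to a survey sent late can record baseline spending after the program has begun. The missed-diary rule would not catch this, because a diary completed after session 1 is not a missed diary. Conversely, a participant who replies a day late to a survey sent early can have a full set of clear evenings and apparently receive no diaries, and so drop out of the spending analysis.

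**Working it through.** **Inputs.** Survey sent *s* days before session 1, with *s* at most 14 and no stated minimum (section 12.0). Reply *r* days after sending, on time if *r* ≤ 7 (section 12.0). Five consecutive diary evenings (section 12.0). At least 3 of 5 diaries needed (section 17.0). The plan does not say whether the first diary falls on the evening of the reply or the next evening, so both are shown: *o* = 0 or 1.

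**The plan's own figures.** The multiplier is 30/k for k completed diaries: 30/5 = 6 and 30/4 = 7.5, as section 17.0 states. At the 3-diary minimum it is 30/3 = 10.

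**Clean baseline days.** Call session 1 day 0 and count day 0 as not clean. The first diary is on day −s + r + o, so the number of diary days before session 1 is s − r − o, limited to the range 0 to 5. For an on-time reply on day 7 to leave all five, s must be at least 7 + 5 + o: 12 days (same evening) or 13 days (next evening).

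**On-time reply on day 7:**

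| Sent, days before session 1 | Clean days, same-evening start | Clean days, next-evening start |
|---|---|---|
| 14 | 5 | 5 |
| 13 | 5 | 5 |
| 12 | 5 | 4 |
| 11 | 4 | 3 |
| 10 | 3 | 2 |
| 8 | 1 | 0 |

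**Late replies, clean days that would be available (same / next evening):**

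| Sent, days before session 1 | Day 8 | Day 9 | Day 10 | Day 11 |
|---|---|---|---|---|
| 14 | 5 / 5 | 5 / 4 | 4 / 3 | 3 / 2 |
| 13 | 5 / 4 | 4 / 3 | 3 / 2 | 2 / 1 |
| 12 | 4 / 3 | 3 / 2 | 2 / 1 | 1 / 0 |
| 11 | 3 / 2 | 2 / 1 | 1 / 0 | – |

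So at least 3 clean days remain for some late repliers at leads of 11 to 14 days (same evening) or 12 to 14 days (next evening).

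**Longest possible overlap.** If the survey is returned on day −1 and diaries start the next evening, they run from day 0 to day +4. Sessions are weekly, so the set ends before session 2 on day 7.

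**Effect on the estimate.** Let B be mean daily spending before the program, D the daily reduction by follow-up, m the number of the five baseline diaries dated on or after session 1, and f the fraction of D already present on those days. The baseline diary component is 6 × (5B − m·f·D) = 30B − 6·m·f·D. The follow-up component is 30(B − D). The observed reduction is 30D − 6·m·f·D = 30D × (1 − m·f/5). For a survey sent 8 days ahead and answered on day 7, m is 4 or 5, so that participant's change shrinks by the factor 1 − 0.8f or 1 − f. If f = 0 there is no bias. The documents give neither f nor the share of participants with m above 0.

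**The case against.** The best defence is that the stated windows fit together: 7 days to reply plus 5 diary days is 12, inside two weeks. Cohorts are scheduled in advance and mostly monthly, so sending close to 14 days ahead is feasible. A reader might infer that on-time participants routinely record baseline spending after the program starts. The documents do not support that: every overlap case needs a later send date, which the text permits but does not describe. What remains is that nothing requires the longer lead, and no registration cutoff before session 1 is stated.

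A reader might also infer that late repliers are expressly barred from diaries. The wording is permissive, written to keep such people in the study. That they get no diaries is the likely reading, given the next sentence about outcomes other than cost, but it is an inference. So is reading the timeline as the 7-day request, although no other timeline is asked for the survey.

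Nor do the documents show an established bias toward zero. They do not say how far session 1 alone would change spending, and exposure cannot go beyond that session if the survey is returned before it. The two faults also mostly arise at different leads: both occur at the same lead only at 11 days (same-evening start) or 12 days (next-evening start).

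Finally, a strict date rule costs participants in a study of 60 that already uses complete cases. That is fair, and is why the fix includes a sensitivity analysis.

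**Conclusion.** The point holds as a conditional gap in the rule. Followed as written, section 12.0 lets diary days on or after session 1 count as baseline whenever the lead is under 12 or 13 days and the reply comes late enough within the 7 days. At leads of about 11 to 14 days it also appears to drop some people who still have 3 to 5 clean evenings. With a lead of 13 to 14 days, no on-time participant is affected by overlap.

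The reach is limited to the diary component of out-of-pocket spending. The irregular monthly items come from the baseline survey, which is meant to be completed before session 1, and the self-efficacy and resourcefulness comparisons are untouched. How much weight this carries depends on which of the plan's two labels for the spending outcome applies. The size of any bias is unknown. Dilution toward zero assumes that session 1 already lowers spending, and the day counts treat the evening of session 1 as after the start; a session held later that evening would shift them by one day.

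**What to change.** In section 12.0:
- Send the baseline survey at least 13 days before session 1 where registration allows.
- State whether the first diary is due on the evening of the reply or the next evening.
- Offer diaries to anyone who returns the survey with at least 3 evenings left before session 1, whether or not the 7-day request was met.

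In section 17.0:
- Count only diary days dated before session 1 as baseline, treat later ones as missed, and apply the existing 30/k multiplier and 3-day minimum.
- Report a sensitivity analysis that keeps the later days, and the number of participants who have any.

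Section 17.0 notes, in the 8/2023 modification, that survey collection was still ongoing. For data already collected, the date filter can be applied at analysis, assuming diary and session dates are on file. Late repliers who were not sent diaries cannot be recovered.

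The cost is wording in two sections and a date filter. Participants with fewer than 3 days before session 1 leave the main spending analysis: for example, a survey sent 10 days ahead and answered on day 7 with a next-evening start leaves 2. Those with exactly 3 have no tolerance for a missed diary and carry a multiplier of 10, so their monthly figures will be noisier.

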See above. Participants will also be able to contact the study team directly, such as by calling or emailing the research assistant after seeing a study flyer or social media post. If this occurs, the study team member will not only complete study eligibility procedures,

but register participants in the Eventbrite system to reserve a CONFIDENCE spot for them. For those caregivers who receive a letter or phone call from the PI or who sign up on the Banner Health Institute site, the PI will contact the participant by telephone and/or email up to 3 times to share more information about the study and/or enroll the participant.

3. Describe the feasibility of recruiting the required number of suitable research participants within the agreed recruitment period. For example, how many potential research participants do you have access to?

USC will complete 12 cohorts of the CONFIDENCE intervention from September 2022 to June 2023, where cohorts will be held monthly except for 3 months where USC will run 2 cohorts simultaneously. We expect to enroll N=5 caregivers per cohort, or about 1/3 of caregivers who sign up to attend the program, to reach our recruitment goal N=60 caregivers.

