Satisfaction Surveys Satisfaction surveys, included in the first follow up survey sent to participants, will be used to examine participant satisfaction with the CONFIDENCE intervention. Participants will be asked about the program's relevance to their care situation, quality of information presented, satisfaction delivery, and enjoyment of the program overall. Each question is asked as a statement to which participants can indicate the extent to which they agree on a 5-point Likert scale. To analyze scale items, we will provide a percentage of each response (e.g., 80% of caregivers "Agreed" or "Strongly Agreed" with this statement).

Fidelity Reports Fidelity reports will be evaluated using total scores averaged across all CONFIDENCE Lessons observed. We will be report these in aggregate and separated by facilitator and observer reports. We will divide reports by scores for adherence and quality. Scores will be reported using a percentage, as prior reports indicate 80% or more on fidelity scores indicates acceptable levels of fidelity. In addition—to examine variability in scores—we will also report this information using means and standards of deviation. **Qualitative Interviews**

Qualitative interviews will be transcribed verbatim and identifying information removed. For interviews conducted in Spanish, interviews will be translated by a native speaker. To conduct our thematic analysis, at least two members of the research team will read at least 2 transcripts and will decide on a preliminary codebook.³⁹ The codebook will be applied to an interview and refined further prior to applying codes to the remaining interviews. At least two coders will analyze each transcript independently and will meet to compare codes and discuss differences in coding until agreements met. A second round of coding will be conducted to integrate new codes added during coding. **Statistical Power and Same Size** Our goal is to recruit at least N=60 of these caregivers into a research study to test preliminary efficacy. This N supports our ability to detect a small to moderate effect size in a two-tailed t-test at alpha=0.05 at 80% power.

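### The fidelity lesson is drawn with no stated balance across cohorts, so a whole lesson may go unscored; separately, the score describes announced lessons only

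*Combined protocol and SAP*

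**What the plan says.** The relevant text is in three sections of the combined protocol and SAP.

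- **Section 12.0, Fidelity.** "We will monitor one randomly selected CONFIDENCE lesson for each cohort". The lesson is picked with a random number from Stata. Nothing is said about spreading the picks over the lessons from one cohort to the next. On notice: "The facilitators will know in advance of each lesson if selected for monitoring so they may record lesson". How long beforehand is not stated. The facilitator rates the selected lesson in a survey sent within 24 hours, and the PI or research assistant scores the recording within two weeks.
- **Section 12.0, Intervention.** "There are five sessions (5 weeks) total to the CONFIDENCE program", and each session has its own topic.
- **Section 17.0, Fidelity Reports.** "Fidelity reports will be evaluated using total scores averaged across all CONFIDENCE Lessons observed". Results are given in aggregate and by rater, divided into adherence and quality, as percentages with means and standard deviations. Prior reports are cited to the effect that "80% or more on fidelity scores indicates acceptable levels of fidelity". No count or score by lesson is planned.

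The number of draws comes from section 8.0: "USC will complete 12 cohorts of the CONFIDENCE intervention from September 2022 to June 2023". The same sentence adds that "cohorts will be held monthly except for 3 months where USC will run 2 cohorts simultaneously".

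**The concern.** Two separate matters arise, and they act in different ways.

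The first is the draw. Lessons on different topics are not interchangeable for judging delivery. If each cohort's lesson is picked without regard to earlier cohorts, some lessons can be scored several times and others not at all. The average then reflects the lessons that happened to come up, and nothing in the report would show it. If a lesson is never scored, the study has no fidelity evidence for that part of the program.

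The second is the notice. Random selection lets scored lessons stand for unscored ones only if both are delivered alike. A facilitator who knows beforehand which lesson will be scored can prepare for it. The facilitator's self-rating covers the same lesson, so neither source of fidelity data describes an unannounced session.

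What is at stake is how far the fidelity figure can be used to say that the program was delivered as designed. In a single-arm pilot, that helps in reading any pre-post change.

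**Working it through.** **Step 1: the plan's own figure.** Section 8.0 gives 12 cohorts and says "We expect to enroll N=5 caregivers per cohort". 12 × 5 = 60, which reproduces the recruitment goal. The calendar in the same paragraph gives a different cohort count: September 2022 to June 2023 is 10 months, and 7 × 1 + 3 × 2 = 13. Both counts are carried below.

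**Step 2: share observed.** 12 cohorts × 5 lessons = 60 delivered lessons, of which 12 are scored: 12/60 = 20%.

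**Step 3: coverage.** Assumption: one independent draw per cohort, each lesson having probability 1/5.

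- A named lesson is never drawn in 12 cohorts: 0.8^12 = 0.0687, or 6.9%.
- At least one of the five is never drawn, by inclusion-exclusion:
 5(0.8^12) − 10(0.6^12) + 10(0.4^12) − 5(0.2^12) = 0.34360 − 0.02177 + 0.00017 − 0.00000 = 0.3220, or 32.2%. One million simulated sets of draws also gave 32.2%.
- In the same simulation, some lesson was observed at most once in 91% of sets, and two or more lessons were missed in 2.2%.

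| Cohorts | Chance that at least one lesson is never observed |
|---|---|
| 10 | 47.7% |
| 11 | 39.4% |
| 12 (stated) | 32.2% |
| 13 (calendar) | 26.2% |

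With a balanced list (2, 2, 2, 3, 3 in 12 cohorts) the chance is 0%.

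**Step 4: direction.** With probability 1/5 for each lesson, the expected score is the plain average of the five lesson means. Imbalance in the realized draw adds variance but has no direction.

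**Step 5: precision, for illustration.** The documents give no fidelity standard deviations. Assume a residual SD of 8 points and a between-lesson SD s.

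- Independent draws: SE = √[(s² + 64)/12].
- Balanced draw: the lesson weights are 2/12 (three lessons) and 3/12 (two lessons). Their squared deviations from 1/5 sum to 3(0.0333²) + 2(0.05²) = 0.00833. With the lessons that get three draws chosen at random, SE = √[64/12 + 0.00833 × (5/4)s²].

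| Assumed lesson SD | SE, independent | SE, balanced |
|---|---|---|
| 5 | 2.7 | 2.4 |
| 8 | 3.3 | 2.4 |
| 10 | 3.7 | 2.5 |

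**Step 6: notice.** No score, reactivity figure or lead time is given, so no effect can be computed. If notice raises scores by b points, an observed 80% corresponds to usual delivery of 80 − b. For an assumed b of 0 to 10, that is 80% down to 70%.

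**The case against.** The case for leaving the plan alone has real weight.

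- **Fidelity is supporting information.** Section 2.0 states efficacy objectives, and the design statement in section 12.0 names efficacy, acceptability and feasibility, with fidelity data collected alongside. The 80% figure is a cited benchmark, and no success rule or test depends on it. This stands, and it keeps the point minor.
- **No lesson-specific result is planned.** A missed lesson therefore invalidates no promised estimate, and the chance that all five are seen is 68%. This is true, but the average is presented as describing the program, and about a one-in-three chance of omitting a topic can be removed at almost no cost.
- **The lack of balance is inferred from silence.** A random number generator can drive a stratified draw. This also stands: if balancing is intended, one sentence settles the matter.
- **Notice has a stated practical purpose.** It allows the lesson to be recorded, and only one lesson per cohort is recorded.

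A reader might infer more than the text supports in two ways. One is that the score is biased upward, with the unbalanced draw as part of the cause. Equal-probability selection causes no such bias, and for the notice the documents support only that the score is open to it.

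The other is that hiding the selection until the session opens would cure the problem. It would not do so cleanly. The facilitator would still know that the session was being recorded. A recording missed at short notice would cost that cohort its only observer score. Concealment also fails by elimination whenever the fifth lesson is the one selected, which happens in 1/5 of cohorts (12 × 0.2 = 2.4 of 12). Balancing in blocks of five would make this worse if facilitators recur and recognize the blocks, an assumption on which the documents are silent. The expected number known by elimination would then be 2(1/5 + 1/4 + 1/3 + 1/2 + 1) + 1/5 + 1/4 = 5.0 of 12.

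**Conclusion.** The point holds as a minor one, in two separate parts.

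- **Coverage and precision.** With independent, equal-probability draws, there is a 32% chance over 12 cohorts (26% over 13) that at least one lesson is never observed, and the average weights lessons by chance. This rests on reading the plan's silence about balancing as independent draws. The loss of precision is illustrative because its standard deviations are assumed.
- **Announced lessons.** The score is open to upward bias of unknown size. The documents do not show that such bias is present, and they give no basis for attaching a number to it.

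The paired tests of the primary and secondary outcomes do not use the fidelity score and are unaffected.

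**What to change.** 1. **Balance the draw.** In section 12.0, replace the cohort-by-cohort pick with a random permutation of one list in which each lesson appears two or three times: 2, 2, 2, 3, 3 for 12 cohorts, or 2, 2, 3, 3, 3 for 13. Choose at random which lessons get the extra place. Permuting the whole list makes the next lesson harder to guess than blocks of five would.
2. **Report the coverage.** In section 17.0, add the number of times each lesson was observed. If cohorts have already run, assign the remaining draws to the lessons seen least. If none remain, the counts alone will show any gap.
3. **State the limitation.** Say in the report that facilitators knew beforehand which lesson would be scored, that the score describes announced lessons, and that reaching 80% is not evidence about routine delivery.
4. **Reconcile the cohort count** in section 8.0 (12 stated, 13 from the calendar), since it sets the length of the list.

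The cost is a few lines of Stata, one small table and one sentence of text, with no extra recordings or raters. Shortening the notice is optional. It would reduce the scope for preparation but would not remove awareness of recording, and it should be adopted only if the team accepts the risk of losing a cohort's only recording.
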